Population defined through inclusion/exclusion criteria to reflect the targeted patient population. Analysis will be performed on all randomized patients who received at least one dose of study drug.

B. Treatment:

Zimura 2 mg versus Sham.

C. Primary variable:

Mean rate of growth (slope) of the square root of GA area over 12 months.

D. Intercurrent events (ICE's) and strategies:

1. Treatment changes (i.e., interruptions, non-adherence, dose changes, discontinuation): “treatment policy” – i.e., treatment changes will be ignored and all data collected will contribute to the analysis regardless of whether or not these follow such ICE's.
2. COVID-19: “treatment policy” – i.e., impact of COVID-19 pandemic will be ignored and all data collected will contribute to the analysis regardless of whether or not these follow such ICE's.

E. Population-level summary:

Difference between groups in mean rate of growth (slope) of the square root of GA area over 12 months.

[figure not shown]
The primary estimator is described as follows.

A mixed model for repeated measures (MMRM) will be applied to all available data, using as response variable the square root of GA area measured by FAF in at least 3 time points: Baseline, Month 6, and Month 12. The MMRM will be used to assess the difference between the treatment groups in terms of the rate of growth of the square root of GA area (slope) over 12 months. Previous trial OPH2003 (GATHER1) showed the change in the square root of geographic atrophy to be remarkably linear over time. As a result, a linear model is not only convenient and easily interpretable, but it is also appropriate given the natural history of the disease. A model will be fitted by using restricted maximum likelihood (REML) and include Baseline VA (< 50 letters vs. ≥ 50 letters), and pattern of FAF at the junctional zone of GA (none/focal vs. banded/diffuse) as used in the randomization as covariates. For the model, fixed effects will include time, treatment, Baseline VA (< 50 letters vs. ≥ 50 letters), pattern of FAF at the junctional zone of GA (none/focal vs. banded/diffuse), treatment by time interaction, Baseline VA (< 50 letters vs. ≥ 50 letters) by time interaction, and pattern of FAF at the junctional zone of GA (none/focal vs. banded/diffuse) by time interaction. The model will include an unstructured modelling of within-subject correlations. If this analysis fails to converge, alternative structures (e.g., heterogeneous autoregressive, heterogeneous compound symmetry, autoregressive, or compound symmetry, in this order) will be considered. The Kenward-Roger approximation will be used to estimate denominator degrees of freedom. The test of difference between the two arms in the mean rate of growth

CONFIDENTIAL

(slope) of the square root of GA area over 12 months will be assessed by testing the appropriate contrast of the model parameter estimates.

[Redacted content]

CONFIDENTIAL

[Redacted text block]

[Redacted text line]

[Redacted text line]

[Redacted text line]

[Redacted text line]

[Redacted text line]

[Redacted text line]

[Redacted text line]

[Redacted text line]

[Redacted text line]

[Redacted text line]

[Redacted text line]

[Redacted text line]

[Redacted text line]

[Redacted text line]

[Redacted text line]

[Redacted text line]

[Redacted text line]

[Redacted text line]

[Redacted text line]

[Redacted text line]

CONFIDENTIAL

- █ [REDACTED]
- █ [REDACTED]
- █ [REDACTED]
- █ [REDACTED]
- █ [REDACTED]
- █ [REDACTED]
- █ [REDACTED]
- █ [REDACTED]
- █ [REDACTED]
- █ [REDACTED]
- █ [REDACTED]
- █ [REDACTED]

SENSITIVITY ANALYSES

Sensitivity Analyses for Missing Data

For the analyses of the primary outcome, the MMRM analysis does not require data imputation and uses only the observed data. Moreover, assuming that the missing data are MAR, the model yields valid results that are comparable to those obtained by applying MI under the MAR assumption.

Four analyses described by Miller et al. (2001) will be performed for further insight into the potential impact of missing data on the results:

1. the observed means from the active arm and the sham arm will be imputed to patients with missing data in the arm they were allocated to;
2. the average of observed means from the active arm and the sham arm will be imputed to all patients with missing data;
3. the observed mean from the sham arm will be imputed to all patients with missing data.
4. the observed means from the active arm and the sham arm will be imputed to patients with missing data in the opposite arm they were allocated to (a “cross-over” scheme);

These four sensitivity analyses make different assumptions about missing data, and are likely to be increasingly biased against a true treatment effect. A robust treatment effect would be expected to remain statistically significant in analyses 1 to 3, since these are likely to be much less biased than analysis 4 under the assumption of a true treatment effect.

To check the sensitivity of the results of the primary efficacy analysis (using the primary estimator as described in section 7.2) to the MAR assumption, MI based on models compatible with Missing Not At

CONFIDENTIAL

Random (MNAR) missingness mechanisms will be used. Two approaches, using SAS' PROC MI, will be considered:

1. The “shift imputation” approach: for missing values at a particular visit, it will be assumed that their expected value is smaller (shifted) by a specified amount (i.e., a specified shift in the size of GA), than for the observed responses (implying that the missing values are more likely corresponding to smaller changes vs. Baseline than the observed ones). Increasing values of the shift will be explored to investigate the sensitivity of the results. This approach can be applied to data with arbitrary missing data patterns. The “tipping point” is the value of the shift that causes statistical significance to be lost. For a robust treatment effect, the tipping point would be considered an implausible value of the shift used in the missing data imputation.

2. The “pattern-mixture-model imputation” approach: missing values at Month 12 visit will be imputed by using the pattern-mixture-model restrictions. Pattern-mixture models provide a general and flexible framework for sensitivity analyses that allows formulating assumptions regarding missing data in a transparent and clinically interpretable manner. In particular, Complete-Case Missing Value (CCMV) and Neighbouring-Case Missing Value (NCMV) restrictions will be applied.

Of note, these imputation techniques are known to induce potential bias, hence they will be used only for sensitivity purposes.

Sensitivity Analysis for Stratification Error

On Monday November 16, 2020 the Duke Reading Center notified that an error occurred at the reading center in the reporting of fundus autofluorescence (FAF) results used as stratification factors for randomization of eligible patients into GATHER2 (ISEE2008) clinical trial.

As a result, 38 patients randomized with Baseline geographic atrophy size between 4 to 10 mm² were placed in a stratum that included participants with size ≥ 10 mm² rather than being placed in stratum that included participants with size < 10 mm².

To assess the impact of this stratification error, two sensitivity analyses will be done by performing analyses that stratify by 3-level covariates for the Baseline geographic atrophy size. The first analysis will stratify by: < 4 mm² vs. ≥ 4 to < 10 mm² vs. ≥ 10 mm², and the second analysis will stratify by: patients randomized prior to November 16, 2020 vs. < 4 mm² vs. ≥ 4 mm².

Since November 16th, patients have been stratified correctly as indicated in the protocol based on their baseline geographic atrophy size: < 4 disc areas (10 mm²) vs ≥ 4 disc areas (10 mm²). The minimization procedure was not modified after November 16, 2020, because implementing any changes to this procedure would have meant putting the trial on hold while the changes were being implemented and validated. Furthermore, an inspection by the randomization center of the balance with respect to baseline geographic atrophy size achieved on November 16, 2021 provided reassurance that the minimization algorithm could continue unchanged.

CONFIDENTIAL

Sensitivity Analysis for Observed GA Measurement

The sensitivity of the results from the analyses of observed (non-square root transformed) area of GA over 12 months will be conducted using the same analysis model as specified in section 7.2.

[REDACTED]

[REDACTED]

[REDACTED]

[REDACTED]

[REDACTED]

- [REDACTED]

- [REDACTED]

- [REDACTED]

- [REDACTED]

[REDACTED]

Descriptive Summaries by Visit

The change in score from Baseline will be analyzed as continuous variables. The composite score and the scores of each sub-scales at Baseline and the changes from Baseline will be summarized descriptively by visit and by treatment group using the observed cases (missing values will not be imputed).

[REDACTED]

SUBSET ANALYSES

The trial is not designed to have adequate power to formally test for the presence of treatment by covariate interactions. Thus, true treatment by covariate interactions will likely be missed, unless they are quite substantial. Conversely, should particular subsets of subjects seem to benefit more or less from therapy than the total population, this will not be taken as reliable evidence of a true treatment by covariate interaction, given the likelihood that such an observation could be due to chance alone. With these caveats in mind, exploratory subset analyses will be performed to identify any major effect that might be worth testing in future trials. In a descriptive manner, treatment effect will be presented for subsets created by multiple covariates. Among these covariates will be the stratification factors: Baseline VA (< 50 vs. \geq 50 ETDRS letters), Baseline GA (< 4 vs. \geq 4 disc area), Pattern of FAF at the junctional zone of geographic atrophy (none/focal vs. banded/diffuse) as well as age (<65 vs. 65~74 vs. 75~84 vs. \geq 85), gender (male vs. female) race (American Indian/Alaska Native vs. Black or African American vs. Asian vs. Native Hawaiian/Pacific Islander vs. White vs. Other), and ethnicity (Hispanic or Latino vs. Not Hispanic or Latino).

CONFIDENTIAL

Since these analyses will be considered as exploratory, they will be conducted without any alpha-level adjustment.

SAFETY EVALUATION

All safety analyses will be performed on the safety population. The analyses will be conducted according to the treatment that they actually received. However, subjects who have ever received an injection of Zimura will be analyzed in the Zimura group. Missing values of safety data will not be imputed and safety summaries will be based on the observed cases.

EXTENT OF EXPOSURE

Exposure to study medication will be evaluated for each treatment group with respect to treatment duration (= Last injection date - First injection date + 30, in days), number of subjects treated at each planned visit, total injections received, using descriptive statistics (N, mean, standard deviation, median, minimum, Q1, Q3, maximum).

ADVERSE EVENTS

Adverse events (AEs) will be recorded starting after the first dose of study drug and continuing until 30 days after the last dose or until the last follow-up visit required by the protocol, whichever comes later. AE data will be evaluated for each treatment group.

Only first year AE data will be included in the following analyses. Treatment Emergent Adverse Events (TEAEs) from the first year will be defined as starting after the first dose of study drug until prior to Month 12 injection. If a Month 12 injection does not exist, the end of the first year is defined as the Month 12 visit (or target of 365.25 days after the first dose if no Month 12 visit) or 30 days after the last injection, whichever is later.

All AEs will be coded using MedDRA™ (version 23.0 update) terms.

- An overview of TEAEs will be provided. A second overview of TEAEs will be provided which displays the overall summary of TEAEs by the categories ‘Study Eye’, ‘Non-Study Eye’, and ‘Non-Ocular’. In addition, the number and percentage of patients with TEAEs will be tabulated for each treatment group and in total by system organ class (SOC) and preferred term (PT). The number and percentage of the subjects who experienced at least one TEAE will be included. Subjects will only be counted once for each preferred term. In case that a subject experienced the same event more than once, the worst severity will be presented.
- Tabular summaries of the following AEs will be provided by SOC and PT:
 - Summary of TEAEs
 - All TEAEs regardless of the relationship to study treatment
 - All TEAEs regardless of the relationship to study treatment with frequency of $\geq 5\%$ in any treatment arm.

CONFIDENTIAL

-
- TEAEs related to study treatment
 - TEAEs related to injection procedure
 - TEAEs by the maximum severity grade
 - TEAEs related to study treatment by the maximum severity grade
 - TEAEs related to injection procedure by the maximum severity grade
 - All Ocular TEAEs by study eye and fellow eye
 - Treatment related Ocular TEAEs by study eye and fellow eye
 - Injection procedure related Ocular TEAEs by study eye and fellow eye
 - Ocular TEAEs (study eye) by the maximum severity grade
 - Treatment related Ocular TEAEs (study eye) by the maximum severity grade
 - Injection procedure related Ocular TEAEs (study eye) by the maximum severity grade
 - TEAEs with high level term of cataract conditions by study eye and fellow eye
 - TEAEs leading to discontinuation of study drug
 - Treatment related TEAEs leading to discontinuation of study drug
 - Injection procedure related TEAEs leading to discontinuation of study drug
 - Ocular TEAEs (study eye) leading to discontinuation of study drug
 - TEAEs leading to death
 - Treatment related TEAEs leading to death
 - Injection procedure related TEAEs leading to death
 - Ocular TEAEs have been defined as TEAEs linked to the “Eye Disorders” system organ class and the ‘Intraocular pressure increased’ preferred term.
 - All AEs, including non-TEAEs, will be included in individual subject listings.
 - The listings will include the subject identifier, age, sex, verbatim term, preferred term, eye (N/A/OD/OS/OU), serious (yes/no), date of onset, relative study day of onset, onset before injection, after first injection or after second injection, duration of the event (or continuing), severity (mild/moderate/severe), causality (relationship to study medication/injection procedure), action taken (study drug permanently discontinued: yes/no), treatment (yes/no), and outcome (resolved/not resolved/fatal).
 - The same listings will be provided separately for severe AEs, AEs leading to permanent discontinuation of the study treatment, and for AEs leading to death.

CONFIDENTIAL

SERIOUS ADVERSE EVENTS AND DEATHS

- Treatment-Emergent Serious adverse events (SAEs) will be summarized by system organ class and preferred term. The number and percentage of the subjects who experienced at least one SAE will be included.
- SAE data will be evaluated for each treatment group.
- Tabular summaries of the following SAEs will be provided:
 - All SAEs regardless of the relationship to study treatment
 - SAEs related to study treatment
 - SAEs related to injection procedure
 - Ocular SAEs (study eye) regardless of the relationship to study treatment
 - Ocular SAEs (study eye) related to study treatment
 - Ocular SAEs (study eye) related to injection procedure
- In addition, separate listings will be created for deaths and all SAEs. List for SAEs will include the subject identifier, age, sex, verbatim term, preferred term, eye (N/A/OD/OS/OU), serious (yes/no), date of onset, relative study day of onset, onset before injection, after first injection or after second injection, duration of the event (or continuing), severity (mild/moderate/severe), causality (relationship to study medication/injection procedure), action taken (study drug permanently discontinued: yes/no), treatment (yes/no), and outcome (resolved/not resolved/fatal).

VITAL SIGNS

Descriptive statistics at each time point up through and including the Month 12 visit will be used to display the changes from Baseline for pulse and blood pressure (systolic and diastolic). Mean change of pulse and blood pressure (systolic and diastolic) from Baseline to the last measurement will be provided.

OPHTHALMIC VARIABLES

Ophthalmic Examination. The following ophthalmic examination variables will be analysed by shift table from Baseline to the pre-injection examination on Month 12 or last visit available whichever comes later (normal/abnormal, unless otherwise specified below):

- Examination of the motility
- Inspection of the lids/lacrimal/lashes
- Examination of the conjunctiva/sclera
- Inspection of the cornea

CONFIDENTIAL

-
- Examination of the iris
 - Examination of the pupils
 - Inspection of the lens status (aphakic, pseudo-phakic, phakic; if phakic, nuclear/PSC/cortical 0, 1, 2, 3, 4), including a listing of subjects with a change in lens status for study eye and (separately) for fellow eye
 - Examination for posterior vitreous detachment
 - Inspection of the optic nerve
 - Inspection of the macula
 - Examination of the retinal vessels

The following ophthalmic examination variables will be analysed by shift table from Baseline through Month 12 or last visit available whichever comes later, on a monthly basis (normal/abnormal, unless otherwise specified below), and from pre-injection to post-injection at each monthly injection

- Examination of anterior chamber activity: Cells (0, trace, 1+, 2+, 3+, 4+)
- Inspection for vitreous haze (0, 1+, 2+, 3+, 4+)
- Examination for vitreous haemorrhage
- Examination of the peripheral retina

Intraocular Pressure. IOP will be summarized by visit, including all pre-injection, “IOP after first injection”, and “IOP after second injection” measurements for applicable visits. An additional tabular summary of the percentage of subjects in categories of IOP will be presented by treatment group, visit, and injection time (pre-injection, IOP after first injection, IOP after second injection).

“IOP after injection” is defined as the IOP measurement that is closest in time to the protocol-specified post-injection timepoint (but at least 30 minutes post-injection). If there are two closest measurements equidistant to this timepoint, then the measurement after the protocol-specified timepoint will be used.

Mean IOP over time of all scheduled measurements (pre-injection, IOP after first injection, and IOP after second injection) will be plotted.

CLINICAL LABORATORY DETERMINATION

- All laboratory data will be listed and values falling outside normal ranges will be identified, whether they will be deemed clinically relevant or not.
- Laboratory data will also be summarized in tables presenting values at each scheduled visit up through the Month 12 visit
- Value changes from Baseline to each scheduled visit up through the Month 12 visit

CONFIDENTIAL

-
- A summary table of all analytes with the Baseline mean and the mean change from Baseline to the last value observed
 - A summary table of all analytes with the Baseline median and the median change from Baseline to the last value observed

For the following parameters:

- Hematological parameters (hemoglobin, white blood cells, platelets, neutrophils (absolute numbers), lymphocytes (absolute numbers), monocytes (absolute numbers), eosinophils (absolute numbers), basophils (absolute numbers)),
- Renal function parameters (serum creatinine and BUN),
- Hepatic function parameters (serum bilirubin, alkaline phosphatase, GGT, SGOT/AST, and SGPT/ALT),
- Electrolytes (sodium, potassium, chloride, carbon dioxide, calcium, and phosphate),
- Complete urinalysis parameters (complete urinalysis including specific gravity, protein, blood, etc.),
- Serum pregnancy test (if of child-bearing potential).

Additional urine or serum pregnancy testing may be performed during the course of the study at the discretion of the investigator, or in accordance with local requirements or regulations.

The incidence of subjects with “Notable Laboratory Values” after the first dose of study drug will be evaluated using the criteria for Notable Laboratory Values given below. Only data collected after the first dose of study drug, up to the laboratory data taken at the Month visit (before Month 12 treatment is administered) will be included; if there is no Month 12 visit, data will be included up to a target of 365.25 days after date of first dose, or 30 days after the last dose of study drug, whichever is later.

By-subject listings of all notable laboratory values will also be provided; for each subject who has an analyte with a notable value, all values of that particular analyte taken during the study will be presented in the listing, and the notable value, and any values outside of normal limits, will be identified.

For this “Notable Laboratory Values” analysis, *all* laboratory values after randomization will be taken in account, i.e., any values obtained after Day 1, at unscheduled visits, as well as values from the regularly scheduled laboratory visit at Month 12. Three Notable Laboratory Values tables and accompanying by-subject listings will be presented: (1) notable abnormalities for subjects with normal Baseline results, (2) notable abnormalities for subjects with abnormal Baseline results and (3) notable abnormalities without regard to Baseline abnormalities (i.e., normal or abnormal Baseline results). The table without regard to Baseline abnormalities will be a composite of the previous two tables (normal Baseline, abnormal Baseline).

CONFIDENTIALLab analytes and primary criteria used for Notable Laboratory Values:

a. HEMATOLOGY

- i. Hemoglobin $< 0.75x$ Baseline
- ii. Platelets < 75 or > 750 ($10^9/L$)
- iii. WBC count < 2.5 or > 17.5 ($10^9/L$)
- iv. Neutrophils (absolute) $< 0.5xLLN$ or $> 1.5xULN$
- v. Eosinophile (absolute) $> 1.5xULN$
- vi. Lymphocytes (absolute) $< 0.5xLLN$ or $> 1.5xULN$

b. LIVER FUNCTION

- i. Total bilirubin $> 1.5xULN$
- ii. Alkaline phosphatase $> 1.5xULN$
- iii. ASAT (SGOT) $> 3xULN$
- iv. ALAT (SGPT) $> 3xULN$
- v. GGT $> 3xULN$

c. RENAL FUNCTION

- i. BUN $> 1.3xULN$
- ii. Creatinine $> 1.3xULN$

d. ELECTROLYTES

- i. Potassium $< 0.9xLLN$ or $> 1.1xULN$
- ii. Sodium $< 0.9xLLN$ or $> 1.1xULN$
- iii. Chloride $< 0.9xLLN$ or $> 1.1xULN$
- iv. Carbon Dioxide $< 0.9xLLN$ or $> 1.1xULN$
- v. Calcium $< 0.9xLLN$ or $> 1.1xULN$
- vi. Phosphorus $< 0.9xLLN$ or $> 1.1xULN$

Notable abnormalities for subjects with abnormal Baseline results are subject to the primary criteria above and the following secondary criteria:

a. HEMATOLOGY

- i. Hemoglobin $< 0.75x$ Baseline (same as primary criterion)
- ii. Platelets $< 0.75x$ Baseline or $> 1.25x$ Baseline

CONFIDENTIAL

- iii. WBC count $< 0.75x$ Baseline or $> 1.25x$ Baseline
- iv. Neutrophils (absolute) $< 0.5x$ Baseline or $> 1.5x$ Baseline
- v. Eosinophils (absolute) $> 1.5x$ Baseline
- vi. Lymphocytes (absolute) $< 0.5x$ Baseline or $> 1.5x$ Baseline

b. LIVER FUNCTION

- i. Total bilirubin $> 1.5x$ Baseline
- ii. Alkaline phosphatase $> 1.5x$ Baseline
- iii. ASAT (SGOT) $> 1.5x$ Baseline
- iv. ALAT (SGPT) $> 1.5x$ Baseline
- v. GGT $> 1.5x$ Baseline

c. RENAL FUNCTION

- i. BUN $> 1.3x$ Baseline
- ii. Creatinine $> 1.3x$ Baseline

d. ELECTROLYTES

- i. Potassium $< 0.9x$ Baseline or $> 1.1x$ Baseline
- ii. Sodium $< 0.9x$ Baseline or $> 1.1x$ Baseline
- iii. Chloride $< 0.9x$ Baseline or $> 1.1x$ Baseline
- iv. Carbon dioxide $< 0.9x$ Baseline or $> 1.1x$ Baseline
- v. Calcium $< 0.9x$ Baseline or $> 1.1x$ Baseline
- vi. Phosphorus $< 0.9x$ Baseline or $> 1.1x$ Baseline

ECG

ECG results will be tabulated as “normal” or “abnormal” at each visit, and will be presented in a normal/abnormal shift table between Baseline and each scheduled ECG visit, as well as between Baseline and the last ECG taken. Descriptive statistics will be presented for continuous variables (eg, heart rate and RR, PR, QRS, QT, QTcB and QTcF intervals) at each visit. A by-patient listing will be provided for ECGs which are deemed abnormal.

[figure not shown]

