10.4 Withdrawal from Trial

Patients have the right to withdraw from the trial at any time for any reason. The Investigator (after consultation with the Sponsor) or Sponsor also have the right to withdraw patients from the trial in the event of concurrent illness, adverse events (including pregnancy in female patients), treatment-failure after a prescribed procedure, protocol violations, cure, administrative or other reasons.

Final trial assessments as outlined in the Study Assessments Chart, Section 3, should be performed on all patients who withdraw. Patients who withdraw due to an adverse event should be followed until resolution of the adverse event, or an adequate explanation for the event is obtained.

Patients who withdraw for any reason should have assessments performed according to the Early Withdrawal schedule.

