10.5 Trial Discontinuation

The reason for a subject discontinuing from the trial will be recorded in the source documentation and case report form. A discontinuation occurs when an enrolled subject ceases participation in the trial, regardless of the circumstances, prior to completion of the protocol. The Investigator must determine the primary reason for discontinuation. A discontinuation must be reported immediately to the clinical monitor or his/her designated representative if it is due to a serious adverse event (SAE) (see Section 12.3). The final evaluation required by the protocol will be performed at the time of trial discontinuation. The

Investigator will record the reason for trial discontinuation, provide or arrange for appropriate follow-up (if required) for such patients, and document the course of the subject's condition.

Premature termination of this clinical trial may occur because of a regulatory authority decision, change in opinion of the IRB/EC, drug safety problems, or at the discretion of IVERIC bio.

The study will be considered completed when the last subject completes the final study visit.

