CONFIDENTIAL

Descriptive statistics will be tabulated as follows:

- Categorical data will be summarized in contingency tables presenting frequencies and percentages.
- Continuous data will be summarized using number of non-missing values (n), mean, standard deviation, median, minimum, 1st quartile (Q1), 3rd quartile (Q3), and maximum values.

Listings with individual subjects' data will be provided for all CRF (including derived data) and central laboratory data or other external data. Data collected in the CRF that are *not* present in a table will also be listed (e.g., time and method of tonometry, comments fields, data on Fatal Outcomes page, etc.).

Visit Windows

The scheduled visits will be used in the analyses over time.

Missing scheduled follow-up visits will be substituted by an unscheduled or early withdrawal visit occurring within each follow-up visit window, if there is only one unscheduled or early withdrawal visit occurring within the window. If there are multiple unscheduled or early withdrawal visits occurring within the window, the closest one within the visit window will be used. If no unscheduled or early withdrawal visit occurred within the window, the visit will be considered as missing. The *details* are tabulated in **Appendix 1**.

Procedures for Minimizing the Occurrence of Missing Data

Of note, the proper approach to address missingness is the prevention of missing data. The sponsor will implement aggressive proactive approaches to minimize the number of patients who are not assessed at 12 months. Among these approaches are the following:

- The study protocol properly distinguishes between reasons for nonadherence (that is, for not receiving randomized therapy and hence for being “off study treatment”) versus nonretention (that is, for not obtaining outcome information and hence for being “off study”). There are only 2 valid reasons a patient can be off study: withdrawal of consent or the achievement of all required efficacy and safety end point information
- The term ‘withdrawal of consent’ is used only when the patient no longer wishes to participate in the trial and no longer authorizes the investigators to make efforts to continue to obtain their outcome data
- Patients are educated during the informed consent process about the continued scientific relevance of their data even if they discontinue treatment, as well as the deleterious effect that missing data has on trial integrity and credibility

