- To enable proper ITT analyses, all patients will be followed until death or trial completion, even if off they discontinue study treatment or initiate other treatment

CONFIDENTIAL

- Creative and effective procedures are being implemented during enrollment and follow-up to enhance achieving targeted levels of retention.
- An oversight process by the sponsor is in place during trial conduct to ensure the achievement of performance standards, including targeted levels of data capture.

Handling Missing Data in Efficacy analyses

Methods that take into account the presence of missing data and that yield valid estimates under the assumption of data missing at random (MAR) will be used. In particular, a Mixed Model for Repeated Measures fitted by Restricted Maximum Likelihood method will be used in the primary analysis, where as-observed data will be used with no imputation. Multiple-imputation will be used in sensitivity analyses, whenever necessary, to impute the missing data, as described in Section 7.4.

Handling Missing Data in Descriptive Analyses

When summarizing categorical variables, subjects with missing data are generally not included unless otherwise specified. When needed, the category of “Missing” is created and the number of subjects with missing data is presented.

When summarizing continuous variables, subjects with missing data are not included in calculations. No imputations are made.

Handling Missing or Partially Missing Dates

Missing or partially missing dates will not be imputed at data level. However, assumptions for missing or partially missing dates for important variables will be made to allow inclusion of appropriate data records in the analyses. In general, the assumptions about the missing or partially missing dates, when needed, are made conservatively to avoid overestimation of treatment effect and underestimation of adverse effects.

If a medication date or time is missing or partially missing, so it cannot be determined whether it was taken prior or concomitantly, it will be considered both as a prior and a concomitant medication.

If the partial AE onset date information does not indicate whether the AE started prior to treatment or after treatment, the AE will be classified as after the start of treatment.

[REDACTED]

[REDACTED]

[REDACTED]

[REDACTED]

[REDACTED]

[REDACTED]

[REDACTED]

[REDACTED]

[REDACTED]

[REDACTED]

CONFIDENTIAL

[Redacted Section Header]

- | [Redacted list item 1]
- | [Redacted list item 2]

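### The Year 1 SAP credits the protocol with a follow-up rule that Protocol 10.4 and 10.5 do not contain, so imaging may be lost for patients withdrawn without withdrawing consent

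*SAP*

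**What the plan says.** The Year 1 SAP, under Procedures for Minimizing the Occurrence of Missing Data, makes three statements. The first is about the protocol: "The study protocol properly distinguishes between reasons for nonadherence" and reasons for nonretention. The second is that "There are only 2 valid reasons a patient can be off study": the patient withdraws consent, or all required endpoint information has been obtained. The third is a commitment: "To enable proper ITT analyses, all patients will be followed until death or trial completion", including patients who stop study treatment or start another.

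Protocol 10.4 says that the investigator, after consulting the sponsor, or the sponsor itself, "also have the right to withdraw patients from the trial in the event of concurrent illness, adverse events", and goes on to treatment failure, protocol violations, cure, administrative and other reasons. Protocol 10.5 defines discontinuation as ceasing to take part in the trial before completing it, and adds that "The final evaluation required by the protocol will be performed at the time of trial discontinuation". Withdrawn patients have the Early Withdrawal assessments, which include FAF (Protocol 10.2.3.49).

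The primary estimand in the Year 1 SAP applies a treatment-policy strategy to treatment changes, including discontinuation. The estimator is an MMRM fitted by REML to observed data, valid under missing at random (MAR), with no imputation. The Year 2 SAP (4.2.1.1) uses the same strategy.

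**The concern.** A treatment-policy estimand needs outcomes measured after treatment stops. The SAP's follow-up commitment would supply them, but sites work from the protocol, and the protocol does not carry that commitment. A patient withdrawn under Protocol 10.4, for example for an adverse event, can leave the trial with one last visit although consent to further visits was never withdrawn.

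The Early Withdrawal image does not close the gap. Under Visit Windows in the SAP, it replaces a missing scheduled visit only if it falls inside that visit's window; otherwise the visit counts as missing. At best it saves one time point, taken close to treatment.

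For such a Zimura patient the MAR model fills the rest of the year, implicitly, with growth like that of Zimura patients who remained under observation. That is close to the effect had treatment continued, which is not the stated estimand. If growth returns towards the Sham rate after injections stop, the error favours Zimura.

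**Working it through.** **Text comparison**

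- Valid reasons to be off study. SAP: two. Protocol 10.4: an open list of investigator or sponsor decisions, in addition to the patient's own right to leave.
- Follow-up after injections stop. SAP: to death or trial completion. Protocol 10.5: one final evaluation at discontinuation. Protocol 10.3 tells patients who develop wet AMD in the study eye to carry on as scheduled, but no visible section gives a parallel instruction for patients who stop injections.

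The SAP's description of the protocol therefore does not match the protocol.

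**The plan's own power figures**

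Inputs from Protocol 11.3 and the SAP sample-size text: about 400 patients randomized 1:1 (200 per arm), true effect 0.11 mm, smallest significant estimate 0.057 mm, power 97% at two-sided 0.05 and nearly 90% at 0.01. The SD is not given as a number.

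- SE = 0.057/1.96 = 0.0291 mm. Implied SD = 0.0291 × √(200/2) = 0.291 mm.
- Power at 0.05 = Φ(0.11/0.0291 − 1.96) = 96.6%, against 97% stated.
- Power at 0.01 = Φ(0.11/0.0291 − 2.576) = 88.6%, against nearly 90% stated.

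The figures reproduce. The check rests only on the ratio 0.11/0.057, so it does not show whether dropout was allowed for.

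**Illustrative bias**

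The documents give no withdrawal rate. Assume that a fraction p of the Zimura arm is removed at Month 6 without withdrawing consent and then grows at the Sham rate. Each such patient has the 0.11 mm/year benefit for half the year, so contributes 0.11 × 0.5 = 0.055 mm.

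- Treatment-policy effect = (1 − p) × 0.11 + p × 0.055.
- A MAR fit to on-treatment data still targets about 0.11, so overstatement = 0.055 × p.

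| p | Policy effect (mm) | Overstatement (mm) | Share of 0.11 | Share of SE 0.0291 |
|---|---|---|---|---|
| 5% | 0.10725 | 0.00275 | 2.5% | 0.09 |
| 10% | 0.1045 | 0.0055 | 5% | 0.19 |
| 20% | 0.099 | 0.011 | 10% | 0.38 |

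If removal came near Day 1 instead, the policy effects would be 0.1045, 0.099 and 0.088 mm, so each overstatement doubles.

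**Power**

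Losing 5, 10, 15, 20 or 25% of patients in both arms outright, with the effect still 0.11 mm, inflates the SE by 1/√(1 − loss). Power becomes 95.8, 94.8, 93.7, 92.3 and 90.6%. The issue is what is estimated, not power.

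**Do the planned sensitivity analyses test this?**

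- Sham-mean imputation (the third of the four Miller analyses) bears on it, but it is single imputation applied to everyone with missing data.
- The shift analysis assumes that missing values reflect smaller growth than observed ones and does not name an arm. The worry here is faster growth in withdrawn Zimura patients, so as written it points the wrong way.

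**The case against.** Much can be said for the plan, and most of it stands as a limit on the point.

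- Withdrawal under Protocol 10.4 is a discretionary right. Neither 10.4 nor 10.5 says that stopping injections ends follow-up, and Protocol 11.7.6 counts permanent stops of trial medication separately. The protocol is silent on off-treatment visits; it does not forbid them.
- The two-reason rule sits in the text on preventing missing data. The estimand definition neither states nor cites it, and the SAP elsewhere speaks of targeted retention levels and relies on MAR.
- The SAP already reports discontinuation of treatment and of the study separately (Disposition of Subjects; Year 2 SAP 4.1.6). It also plans Sham-mean and cross-over imputation, tipping-point and pattern-mixture analyses.
- Consent pages and the visit-window appendix are not in the public copy, so actual retention practice cannot be judged.

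A reader might infer that the estimand assumes full retention and that post-treatment data will be missing. The documents do not support that: the data may be missing, only for patients actually withdrawn, in unknown number. A reader might also take 5% to 10% as the expected bias. That too goes beyond the evidence. The fraction is assumed, and only patients removed without consent withdrawal belong in it, since those who withdraw consent would be lost under any rule.

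None of this makes the SAP's account of the protocol accurate, and the follow-up it promises has no matching instruction to sites.

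**Conclusion.** The point holds as a contradiction between documents with a consequence for the primary estimand. The SAP attributes to the protocol a separation and a follow-up rule that Protocol 10.4 and 10.5 lack. Applied as written, the protocol can end imaging that the treatment-policy estimand needs.

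Confidence is high on the text and low on the size. The illustrated overstatement of 0.003 to 0.011 mm rests on removal at Month 6, an immediate and complete return to Sham growth, assumed fractions of 5% to 20%, and no post-withdrawal images. It stays below 0.4 of the implied standard error, with little effect on power. No figure was derived for Year 2, where the same strategy applies.

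**What to change.** Reconcile Protocol 10.4 and 10.5 with the SAP's missing-data section. State in the protocol that stopping injections does not by itself end the scheduled FAF and BCVA visits unless the patient withdraws consent. This takes no position on when or why treatment should stop. The cost is a protocol clarification, a letter to sites, and already scheduled visits for the patients concerned; no new procedure is needed.

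If the protocol is not changed, or follow-up is already over (the Year 2 SAP says that the Year 1 primary analysis has been done), correct the SAP's statement about the protocol. Report the planned Sham-mean imputation prominently, preferably with a Sham-reference-based multiple imputation for Zimura patients after withdrawal. That costs programming time only. Separate recording of treatment and study discontinuation is already planned and need not be requested.
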